6. RECRUITMENT, RANDOMISATION AND TREATMENT OF PATIENTS

Summaries of patient assessments can be found in Appendices 1 and 2.

6.1 PRE-RANDOMISATION

6.1.1 Consent and enrolment

Following confirmation of eligibility, patients who are willing may have consent taken for trial participation. This should be done by a clinical member of the trial team. Further details on consent are given in section 9.7 below. Patients who have signed the trial consent form are deemed to have been “enrolled”. Due to the general need for urgent treatment of pleural infection, trial consent should take place on the same day as baseline assessment and randomisation.

6.1.2 Baseline assessment

The baseline assessment should be performed by a clinical member of the trial team. This will include collection of the following data:

- Patient demographics
- Past medical history
- Details of current pleural infection, including symptoms and treatment
- Standardised thoracic ultrasound scan
- Results of relevant recent radiology
- Results of relevant recent blood tests
- EQ-5D quality of life health questionnaire

Patients who have not had a chest radiograph (ideally P-A) performed within the two days prior to the baseline assessment should have this done before they undergo their allocated procedure.

Patients who have not had relevant clinical blood tests (as defined in section 6.4.1) performed within one day of the baseline assessment should have these done prior to undergoing their allocated procedure.

6.2 RANDOMISATION AND TREATMENT ALLOCATION

6.2.1 Randomisation

Following baseline assessment, randomisation will be performed by a member of the trial team using a web-based system (Sealed Envelope Ltd). Participants will be randomised in a 1:1 ratio to either the control or the intervention arms of the study. The allocation will be determined following minimisation with a random component. The minimisation factors will be:

- Evidence of fluid complexity on thoracic ultrasound – none or mild vs moderate or severe
- Effusion size - $\geq 50\%$ thorax or $< 50\%$ thorax using visual estimation on chest radiograph

Concealed randomisation will reduce selection bias. The sequence of random allocations will be generated by computer and will be concealed from all clinical and research personnel.

6.2.2 Treatment allocation

In the control arm, patients will undergo standard chest drain insertion. In the intervention arm, patients will undergo a medical thoracoscopy. Further details for both these procedures can be found in the sections below, and in the trial manual.

6.2.3 Blinding

The SPIRIT trial will be conducted on an “open label” basis. As such, treatment allocation will not be concealed from either participants or trial personnel. No attempt at “sham” procedures will be made.

6.3 POST-RANDOMISATION

6.3.1 Control arm

Patients who are allocated to the control arm should undergo chest drain insertion on either the same or following day as they are *diagnosed as needing drainage*. Separate procedural consent must be taken as per local policy. Thoracic ultrasound guidance (either direct vision or contemporaneous marking) should be used for all such procedures. The chest drain may be inserted using either Seldinger or dissection techniques as per local hospital guidelines. It must be of size 16 French or greater and must be secured using at least one skin suture. The drain should be attached to an underwater seal (or digital equivalent), with the rate of initial fluid removal at the discretion of the inserting physician.

Following insertion, samples of pleural fluid should be taken directly from the drain and sent as per section 6.4.2 below. A post-procedure chest radiograph should be performed within 12 hours of drain insertion.

6.3.2 Intervention arm

Patients who are allocated to the intervention arm should undergo a medical thoracoscopy on either the same or following day as they are *diagnosed as needing drainage*. Separate procedural consent must be taken as per local policy. Patients with a small effusion may have an induced pneumothorax performed prior to their thoracoscopy if necessary. The medical thoracoscopy should be performed as per local hospital guidelines, including using thoracic ultrasound where appropriate. Either a rigid or semi-rigid approach is acceptable, as are either single- or dual-port techniques. Conscious sedation may be used at the discretion of the operator. A sample of the pleural fluid which is drained should be sent as per section 6.4.2 below. During the procedure, the patient should undergo breakdown of accessible septations; parietal pleural biopsies; and intrapleural washout. Further details about these interventions may be found in the trial manual. At the end of the procedure, an appropriately-sized chest drain (minimum gauge 16 French) should be inserted and secured to the skin using at least one suture. The drain should be attached to an underwater seal (or digital equivalent) to allow full evacuation of the pleural cavity.

A post-procedure chest radiograph should be performed within 12 hours of completion of the thoracoscopy.

6.3.3 Allocation failures

The nature of a participant's care is at all times the responsibility of the treating physician. However, on any occasion where treatment differs from that specified in the trial protocol then a protocol deviation form should be completed. In addition, patients who do not undergo their allocated procedure will be recorded as "allocation failures." The full reasons for all allocation failures should be recorded.

In the control arm, an allocation failure will refer to any patient who does not have a chest drain performed within the stipulated time window, or does not have a chest drain insertion performed as allocated.

In the intervention arm, an allocation failure will refer to any patient who does not have a medical thoracoscopy within the stipulated time window. Such patients should, in the first instance, aim to have a 16F gauge (or larger) chest drain performed as per the control arm.

If a patient is unable to undergo their allocated procedure, all subsequent tests and follow-up visits should be timed from the day of randomisation.

6.3.4 Post-procedure inpatient period

Whilst an inpatient post-procedure, a patient's care will essentially follow standard practice. As such, on their first day post-procedure patients should undergo a clinical assessment, as well as a chest radiograph and blood tests (as detailed below). Further clinical assessments should then be made as per standard local clinical practice.

Blood tests should be performed on at least alternate days until day 9, and then at least weekly thereafter if the patient remains in hospital.

Thoracic ultrasounds should be performed on day 1 post procedure, and then on days 3 and 7 post procedure (+/- 1 day), and then every 7 days (+/- 1 day) if the patient remains in hospital.

The results of these, as well as the patient's symptoms (as measured by VAS scores) and clinical observations, will be recorded for trial purposes on days 1, 3 and 7 (+/- 1 day), and then every 7 days (+/- 1 day) until discharge or transfer to another hospital for ongoing care.

On day 7 post procedure (+/- 1 day), the patient should be asked to complete the EQ-5D health questionnaire. If the patient has been discharged, this should be completed at home and returned to the co-ordinating trial unit at Bristol.

The need for and timing of drain removal is at the discretion of the treating physician.

6.3.5 Use of intrapleural enzyme therapy

Intrapleural enzyme therapy, such as tPA and DNase, may be used in trial participants (in either treatment arm) at the discretion of the treating physician. As a guideline, however, the use of these agents should follow standard practice and be reserved for those who are continuing to demonstrate evidence of active pleural infection despite intercostal drainage. In all trial patients, the use of enzyme therapy should be considered in the following circumstances:

- Persistent or rising inflammatory markers on the second day post trial procedure
- Persistent or intermittent fevers on the second day post procedure

- Radiological evidence of ongoing fluid collection with no associated fluid output on the second day post procedure

The need for intrapleural enzyme therapy will be recorded as a trial outcome measure.

6.3.6 Referral for thoracic surgery

For some patients, in the event of the failure of the medical treatments described above, a referral for thoracic surgery (e.g. VATS debridement) may become necessary. As before, the use of this option is at the discretion of the treating physician and may be considered in any patient at any time during their treatment course.

The need for referral for rescue surgery will be recorded as a trial outcome measure.

6.3.7 Discharge

The timing of a patient's discharge remains at the discretion of the treating physician. For the purposes of the trial analysis, both the date when a patient is made medically fit for discharge and the date of their actual discharge will be recorded.

6.3.8 Trial follow-up visits

Trial follow-up visits are intended to match the schedule of routine follow-up for patients with pleural infection. As such, participants will be asked to return for assessment on day 30 post procedure (+/- 3 days) and on day 90 post procedure (+/- 7 days).

As part of standard care at these visits, patients should have a clinical assessment, chest radiograph (if not performed within the 7 days before), thoracic ultrasound, and blood tests as described below. They will also be asked to complete the EQ-5D quality of life questionnaire. The results of these tests will be recorded as part of the trial.

Patients who attend their post-discharge follow-up visit outside of the specified windows may still have their data collected, but these visits should be recorded as protocol violations.

For patients who are unable to attend a post-discharge follow-up visit, attempts should be made to contact them over the telephone in order to complete as much of the trial data collection as possible. Patient-reported data, such as the EQ-5D, may be sent by to the patient by post for completion and return to the trial co-ordinating centre.

For patients who remain in the study but can neither attend a visit nor be contacted over the telephone at the appropriate time, as much information as possible should be gathered from either the patient's hospital notes or through contacting community healthcare services.

6.4 BIOLOGICAL SAMPLES

6.4.1 Blood tests

All blood tests performed during the SPIRIT trial are accepted as being part of the standard care of patients with pleural infection. Samples will be processed at local hospital laboratories. Results from these tests will be recorded at the following time points: at the baseline assessment; on the first day after allocated procedure, and every alternate day after that until discharge; at the day 30 follow-up visit; and at the day 90 follow-up visit.

The results recorded at each time point should cover: full blood count, urea and electrolytes, C-reactive protein, and liver function tests. In addition, results for random serum glucose and lactate dehydrogenase should be recorded at the time of baseline assessment.

6.4.2 Pleural fluid

All pleural fluid tests performed during the SPIRIT trial are accepted as being part of standard care. During their allocated procedure, patients in both the control and the intervention arms should have pleural fluid samples sent to the local microbiology laboratory for culture and microscopy processing. A minimum of 5mls of fluid should be sent in both a sterile, universal container and in blood culture bottles.

6.4.3 Pleural biopsy samples

All pleural biopsy samples taken during the SPIRIT trial are accepted as being part of a standard thoracoscopy procedure. For patients in the intervention arm, at least five parietal pleural biopsy samples should be taken at the time of medical thoracoscopy. These samples should be sent in a sterile container (with or without sterile saline) to the local microbiology laboratory for culture and microscopy processing.

6.4.4 Research samples

Patients will be asked if they are willing to consent to up to 200mls of pleural fluid and up to 3 additional biopsy samples being taken for storage, transport and subsequent biomolecular testing. If taken, these samples should be processed and stored as per the trial manual.

6.5 IMAGING

6.5.1 Thoracic ultrasound

All thoracic ultrasound scans are to be performed as part of standard clinical care. Scan results should be documented during the baseline assessment; on the first, third and seventh days post allocated procedure (and then every seven days (+/- 1 day) after that if the patient remains in hospital); and at the time of the day 30 and day 90 follow-up appointments. The scans on days one and three do not need to be completed if they fall outside of normal working hours, but at least one of these assessments must be completed.

Scans should be performed by those with at least Royal College of Radiologists Level One accreditation (or equivalent), or by those with sufficient experience to be equivalent to this standard.

6.5.2 Chest radiography (x-ray)

All chest radiographs performed during the SPIRIT trial are part of standard care. Images should ideally be performed as P-A and are to be taken at or prior to baseline assessment; within 12 hours of the allocated procedure finishing; on the first day post procedure; after drain removal (but before discharge); and at the day 30 and 90 follow-up visits.

6.6 OTHER TESTS

6.6.1 Quality of life

Patients' serial quality of life will be assessed using the validated EQ-5D-5L (EuroQol Research Foundation). They will be asked to complete the document at baseline; on day 7 (+/- 1 day) post procedure; and at the day 30 and day 90 follow-up visits.

6.7 SEMI-STRUCTURED INTERVIEWS OF PATIENT EXPERIENCES

In order to better understand patient (and carer) subjective experiences of recruitment and randomisation procedures, and thus help determine the trial's acceptability, a subset of participants will

be invited to participate in semi-structured interviews. The sample size for the qualitative study is 20 patients (10 from each treatment arm), as this figure is expected to allow data saturation to be achieved.

All patients will be asked at enrolment whether they are willing to be contacted about taking part in an interview. Those who give their consent will be provided with a more detailed, specific patient information sheet regarding the interviews.

Interviews will take place approximately two weeks (14 days +/- 3 days) post trial procedure. Patients will have the option of interview either by telephone or face-to-face in their own home, whichever they feel is more appropriate. Patients who remain in hospital after two weeks may also be interviewed, but this must be done in an appropriate environment as described in Appendix 4. They will be asked to confirm their consent verbally (in the case of telephone interviews) or in writing if face-to-face. Should an additional party (such as a member of their family or a carer) wish to participate, they will be asked to complete a separate consent form.

Interviews will be semi-structured in nature and will last approximately 60 minutes. Interviews will be audio-recorded, transcribed, anonymised and imported into a qualitative data management software package (NVIVO, QSR International Pty Ltd.)

The interviews will employ a topic guide designed to explore patients' views regarding their illness; the trial recruitment process; and the interventions. This will allow areas for refinement to be identified. The topic guide will be developed with patient and public involvement (PPI). Further details regarding semi-structured interviews and their analysis can be found in Appendix 4.

6.8 END OF TRIAL

The trial will close to recruitment when the thirtieth patient has undergone randomisation and treatment allocation, unless the trial steering committee, regulatory bodies or Sponsor recommend stopping before this point. The trial will end with the final follow-up visit, death or withdrawal of the last patient remaining in the study.

7. STATISTICS AND DATA ANALYSIS

7.1 STATISTICAL ANALYSIS

7.1.1 Sample size

The SPIRIT study is a feasibility study and as such there has been no attempt at formal power or sample size calculation. A recently completed prospective observational study of pleural infection patients requiring drainage (32) would suggest that approximately 150 patients in total would be seen by the selected trial centres over the course of a year. Based on a conservative accrual rate of one of every five patients, a sample size of 30 patients will be used as this is felt to be both sufficient to assess practicability and to suggest the presence of possible between-group differences.

7.1.2 Primary outcome analysis

The primary outcome (feasibility) will be assessed in three parts:

- The ability to recruit to the study will be determined by the proportion of the total number of “pre-screened” patients (those with suspected pleural infection seen during the trial period) who are not eligible for trial entry. The primary outcome will be defined as successful if <2/3 of pleural infection patients are recorded as pre-screen failures. This will be a surrogate for whether the trial’s question is applicable to a reasonable proportion of the pleural infection population.
- The ability to randomise patients to the trial interventions will be determined by the proportion of the total number of patients who are offered a patient information sheet (screened patients) who do not proceed to trial enrolment and randomisation. The primary outcome will be defined as successful if <2/3 of those who receive trial information are recorded as screen failures. This will be a surrogate for whether suitable patients are willing to take part in the trial, and whether any delays associated with trial recruitment impact on patient care.
- The ability to deliver the trial protocol will be determined by the proportion of the total number of patients who do not receive their allocated procedure on either the same day as randomisation or the next. The primary outcome will be defined as successful if <50% are recorded as allocation failures in both trial arms, assessed individually. This will be a surrogate for whether the trial centres are able to offer a rapid pleural intervention having committed to doing so.

Trial logs will also be scrutinised for specific reasons which occur regularly for pre-screen, screen, or allocation failures.

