2.3 LAY SUMMARY

A pleural effusion is a collection of fluid in the space between the lung and the chest wall (the pleural cavity). It commonly occurs as a result of pneumonia and can cause significant breathlessness because the lung becomes compressed. In about 10% of cases, this fluid can itself go on to become infected, which increases the chances of someone becoming unwell enough to need surgery, or even dying. To reduce the chance of this happening, it is vital that the fluid is drained away completely as soon as possible after someone is diagnosed with pleural infection. This is usually done by inserting a small chest tube between the ribs and allowing the fluid to come out over period of about 24 hours. This treatment typically requires many days in hospital but is common and generally low risk.

Medical thoracoscopy is a common technique used to diagnose and drain effusions, although it is not routinely used for pleural infection in the UK as it tends to be reserved for those who are suspected of having cancer. It involves inserting a small camera between the ribs into the fluid and can be done under local anaesthetic. The procedure is very safe, but carries a slightly higher risk of complications than standard chest tube insertion. However, the main benefit of the procedure is that it can allow a patient to spend less time in hospital because the chest is drained completely all at once.

This study, the SPIRIT trial, is designed to see if a group of UK hospitals are able to safely offer medical thoracoscopy to patients with pleural infection. It will recruit 30 patients from 7 UK hospitals over a year and will randomly allocate half of them to undergo thoracoscopy and half to the standard chest drain. Over 3 months of follow up, we shall also examine how the treatment affects patients themselves, and whether it is effective at reducing patients' time in hospital or their need for surgery.

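### The criterion labelled as ability to recruit measures eligibility, and no feasibility criterion uses accrual over time, although the plan rests on 30 patients randomised in a year

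*Protocol*

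**What the plan says.** Protocol section 7.1.2 assesses feasibility in three parts, each with its own threshold.

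- **Part 1, ability to recruit.** The text begins "The ability to recruit to the study will be determined by the proportion of the total number of" pre-screened patients and takes the share who are not eligible. The threshold is: "The primary outcome will be defined as successful if <2/3 of pleural infection patients are recorded as pre-screen failures". The section then explains what the ratio stands for: "This will be a surrogate for whether the trial’s question is applicable to a reasonable proportion of the pleural infection population".
- **Part 2, ability to randomise.** "The primary outcome will be defined as successful if <2/3 of those who receive trial information are recorded as screen failures".
- **Part 3, ability to deliver.** "The primary outcome will be defined as successful if <50% are recorded as allocation failures in both trial arms, assessed individually". Its only time element is how soon the procedure follows.

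Section 4.3.1 likewise defines the primary outcome through numbers and proportions of failures.

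The plan itself is stated as a rate. Section 7.1.1 expects that "approximately 150 patients in total would be seen by the selected trial centres over the course of a year", and takes one in five of them to reach 30. The lay summary (section 2.3) says: "It will recruit 30 patients from 7 UK hospitals over a year". Section 6.8 ends recruitment on a count: "The trial will close to recruitment when the thirtieth patient has undergone randomisation and treatment allocation". The exception is an earlier stop recommended by the steering committee, regulatory bodies or Sponsor. The body of the protocol sets no calendar limit.

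**The concern.** The label and the measure of part 1 do not match. A ratio of ineligible to logged patients shows how selective the entry criteria are. It does not show how many patients the centres can randomise in a given time, and section 7.1.2 itself describes it as standing for applicability.

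Sections 2.2.1 and 4.5 say that the study is meant to inform the design of a larger trial. The number of centres and the duration of that trial depend on randomisations per centre per month, and this quantity plays no part in the feasibility verdict. Because recruitment closes at a count, reaching 30 says nothing about speed unless the time taken is also judged. A favourable finding on ability to recruit could therefore be reported after accrual well short of plan, and an unfavourable one after accrual exactly on plan.

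**Working it through.** **Inputs.** From section 7.1.1: about 150 patients seen per year, one in five accrued, 30 in total. From section 2.3: 7 hospitals, one year. From section 7.1.2: thresholds of 2/3 for part 1 and 2/3 for part 2. From section 6.8: closure at the thirtieth randomisation.

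**1. The plan's own figure.** 150 × 1/5 = 30 per year, or 30/12 = 2.5 per month across all centres. This reproduces the stated 30.

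**2. The lowest yield that passes parts 1 and 2.** Let f1 be the pre-screen failure share and f2 the screen failure share. The yield is (1 − f1)(1 − f2). With both shares below 2/3, it must exceed 1/3 × 1/3 = 1/9.

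- At 150 seen per year: 150/9 = 16.7 randomised per year.
- Relative to plan: 16.7/30 = 56%.
- Time to 30 patients: 30/16.7 = 1.8 years.

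An example in whole patients: 266 logged, 89 eligible, 30 randomised. Pre-screen failures are 177/266 = 66.5% and screen failures 59/89 = 66.3%, so both parts pass. At 150 per year, 266 patients represent 266/150 = 1.77 years.

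**3. Lower throughput.** Assume f1 = 60% and f2 = 50%, which give the planned yield of 0.4 × 0.5 = 1/5. The annual numbers below 150 are also assumptions.

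| Seen per year | Randomised per year | Years to 30 | Parts 1 and 2 |
|---|---|---|---|
| 150 | 30 | 1 | pass |
| 75 | 15 | 2 | pass |
| 50 | 10 | 3 | pass |
| 30 | 6 | 5 | pass |

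At the boundary yield with 75 seen per year, accrual is 75/9 = 8.3 per year and 30 patients take 3.6 years, still with a pass.

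**4. The converse.** Take 150 seen in the year, 105 ineligible, 45 eligible and 30 randomised. Part 1 gives 105/150 = 70%, above 2/3, so it fails. Part 2 gives 15/45 = 33%, a pass. The one-year plan is met exactly.

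**5. What accrual itself would show.** Assume a constant rate. If recruitment stops at 30 patients after T years, the exact 95% limits for the annual rate are the 2.5% and 97.5% points of chi-square with 60 degrees of freedom divided by 2T, that is 20.24/T and 41.65/T.

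- T = 1: 30 per year (20.2 to 41.6).
- T = 1.77, the example in step 2: 16.9 per year (11.4 to 23.5), wholly below 30.
- The interval lies wholly below 30 once T exceeds 41.65/30 = 1.39 years.

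If recruitment stops at a fixed date, the Poisson interval applies. Fifteen in one year gives 8.4 to 24.7, which excludes 30. Twenty in one year has an upper limit of 30.9, which does not. Per site-month, if all 7 hospitals are assumed open for 12 months (7 × 12 = 84), the plan is 30/84 = 0.36, and 15 patients give 0.18 (0.10 to 0.29).

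**The case against.** The case for leaving the criteria alone has real substance.

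- Speed of accrual is not declared to be the main question. Section 2.2.1 puts first whether centres have the flexibility for urgent thoracoscopy, and section 7.1.2 says openly what each ratio stands for. This stands, but it supports relabelling part 1: the stated meaning is applicability, while the label is recruitment.
- The accrual rate in section 7.1.1 is itself a proportion, one in five, and parts 1 and 2 bound it. This also stands. A reader might infer that accrual at a quarter of plan would be called feasible whatever the cause. The document does not support that: a yield of 1/20 lies below 1/9 and must fail part 1 or part 2. Very slow accrual passes only when fewer patients are seen or logged.
- A reader might also infer that the chance of passing is unaffected by accrual in every setting. It is not. In a fixed year the denominators shrink: with assumed failure proportions of 40/75 and 20/35, the binomial probability of passing parts 1 and 2 is 0.94 with 150 logged, 0.85 with 75 and 0.73 with 38. The invariance is exact only for given observed proportions.
- Recruitment is not unsupervised. Section 6.8 allows an earlier stop, section 11.2 has the steering committee monitor progress, and the amendment log mentions a trial end date. These are oversight and do not enter the success definition.
- Descriptive accrual could appear in a statistical analysis plan, which was not available. That would not change a verdict whose definition the protocol fixes.

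**Conclusion.** The point holds as a mismatch between label and measure, together with the absence of accrual from the success definition. Parts 1 and 2 guarantee only a yield above 1/9 of logged patients, 56% of the planned 1/5, and do not react to throughput. They can pass recruitment that takes about 1.8 years at the projected 150 per year, or longer if fewer patients are seen, and they can fail recruitment that meets the one-year plan.

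The durations are approximate. Section 7.1.1 counts patients requiring drainage, whereas the pre-screening log in section 5.1.1 takes all suspected infected effusions. The failure proportions and reduced throughputs are illustrative, and the 84 site-months assume that every hospital is open all year, which the protocol does not state. None of these assumptions is needed for the main conclusion, which follows from the form of the three criteria.

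The matter affects what the study may conclude about recruitment. It does not affect participant safety or the data collected.

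**What to change.** In section 7.1.2:

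1. Relabel part 1 as eligibility, keeping its threshold and stated meaning.
2. Base the statement on ability to recruit on observed accrual: time to the thirtieth randomisation (or the number randomised if the trial stops early), and randomisations per open site-month using actual site-opening dates.
3. Give an exact 95% confidence interval matched to the way recruitment ended: gamma (chi-square) limits if it closed at 30 patients, Poisson limits if it closed at a fixed date.
4. Compare the interval with the planned 30 per year, about 0.36 per site-month if all 7 hospitals are assumed open for 12 months. Do not conclude that the trial can recruit at the planned rate when the interval lies wholly below it. An interval that includes the planned rate does not show that the rate was reached: 20 in a year would still include it. The estimate and interval should therefore be reported in either case.

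The cost is a change of wording and one calculation from randomisation and site-opening dates. No new data are needed. The downside is that slow accrual could make the stated feasibility conclusion less favourable.
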